#### 13.1.1.4.5 Duration of Follow-up after Adverse Events

All adverse events should be followed until they are resolved or until a stable clinical endpoint is reached. The occurrence of AEs and SAEs will be monitored until 4 weeks after the EoT visit. Any patient with ongoing SAEs will be followed until recovery or stabilization of the SAE.

COVID-19 specific considerations: All confirmed cases of COVID-19, occurring after the patient has provided informed consent and until 4 weeks after the EoT visit, must be reported as SAE, and reported to column within 24 hours upon knowledge.

The seriousness criterion for COVID-19 hospitalized patients should be "hospitalization"; if the patient was not admitted to a hospital or the event is not resulting in prolonged hospitalization, the seriousness citerion "medically significant" should be used.

In all cases, details of the patient's symptoms, treatment and any clinically relevant information, should be entered in the SAE forms, as appropriate.

#### 13.1.2 Acute Tolerability of L-CsA

Acute tolerability of L-CsA during initial dosing will be determined by measuring spirometry. FEV1 will be measured at prior to dosing with L-CsA. A decline of associated with symptoms could warrant IMP discontinuation.

#### 13.1.3 Infections

Acute infections will be evaluated according to the following criteria:

- Bacterial infection: bacterial infections will be diagnosed by conventional laboratory culture methods in combination with clinical symptoms [Bonvillain 2007]. Pneumonia requires presence of new worsening infiltrates by chest radiography and growth of organisms in Bronchoalveolar Lavage (BAL) or sputum samples with anti-microbial treatment.
- Fungal infection: the revised consensus definitions of the European Organization for Research and Treatment of Cancer / Mycosis Study Group will be used for the diagnosis of fungal infections [De Pauw 2008]. Fungal infections will be classified as proven, probable or possible according to host, clinical and microbiological criteria.
- Viral infection: the diagnosis of viral infection requires a 4-fold increase in serial serum samples and/or one of the following: a newly positive IgM antibody titer associated with clinical signs/symptoms requiring antiviral therapy; sero-conversion; virus isolation; or

histopathologic evidence of viral infection [Bonvillain 2007]. The diagnosis of viral pneumonia requires impairment of either pulmonary mechanisms or gas exchange, or reduction in gas transfer in the appropriate clinical context.

Occurrence of acute infections will be monitored permanently throughout the complete clinical trial period. Sputum and BAL samples will be collected, if indicated, and monitored for the presence of bacterial, viral and fungal pathogens.

An infection is defined as any acute infection requiring antimicrobial therapy. All acute infections will be reported as AEs. Information captured on the AE CRF will include: date of onset, pathogen identified, resolution, and action taken.

In the case of an acute infection episode fulfilling the criteria of a serious adverse event, the reporting timelines as laid down in Section 13.1.1.4 have to be adhered to.

The cumulative incidence of acute infections as well as the number of acute infections per patient will be summarized by treatment group.

The samples should be evaluated by the local certified laboratory of each center. When needed due to unexpected circumstances and upon clinical judgment (e.g. patient travelling, acute event happening in a location distant to clinical center etc.), samples could also be analyzed by a different laboratory as per patient convenience and the related results will be provided to the Investigator.

#### 13.1.4 Malignancies

All malignancies must be confirmed by histopathology. Malignancies will be documented on the AE CRF.

#### 13.1.5 Clinical Laboratory

Laboratory assessments will be performed following the routine protocols at each study visit by the local laboratory at each site.

The following clinical laboratory parameters have to be documented:

- White Blood Cell (WBC) count with differential
- Red Blood Cell (RBC) count
- Platelet count
- Alkaline phosphatase (AP)
- Alanine Aminotransferase (ALT)
- Aspartate Aminotransferase (AST)
- Gamma Glutamyl Transferase (y-GT)
- Blood Urea Nitrogen (BUN)
- Serum bilirubin
- Serum creatinine

Laboratory assessments listed above will be performed at a certified local facility.

#### 13.1.5.1 Pregnancy Test

Serum samples from women of childbearing potential will be collected for pregnancy tests at screening and with all scheduled blood draws. Positive results will be recorded in the eCRF and appropriate actions will be taken. At Visit 1, a serum or urine pregnancy test must be obtained within 7 days prior to randomization. A urine pregnancy test is allowed at this visit so that the result can be obtained rapidly in order to not delay randomization.

#### 13.1.5.2 Cyclosporine A and Tacrolimus Whole Blood Trough Levels

A whole blood sample for the determination of cyclosporine A and/or tacrolimus trough level will be collected at each visit. In patients allocated to L-CsA inhalation, the sample should be collected within 60 minutes before inhalation. The mean cyclosporine A and/or tacrolimus trough level will be compared across treatment groups. Blood samples will be evaluated by the local laboratories.

#### 13.1.5.3 Donor Specific Antibody Test

Serum samples for donor specific antibody testing will be collected at Screening, and at Visits 4, 6, and 9. If a DSA test performed within 4 weeks before screening is available, a further DSA test at screening visit will not be mandatory and the previous result will be reported in eCRF.

#### 13.1.5.4 Renal Function

As lung transplant patients frequently present with symptoms of renal impairment special emphasis is paid for the key parameter of renal function, i.e., serum creatinine. The classification of renal dysfunction shall follow a unique terminology to describe the disorder (Table 7):

#### Table 7. Terminology of renal disorders

Proposed Term	Medical Condition	Preferred Term
Blood creatinine abnormal or Enhanced creatinine level or Increase of creatinine level	Temporarily increased creatinine values due to medical or nutrition condition	Blood creatinine increased
	Continuously increased creatinine values due to medical condition  No treatment required	
Renal impairment	Continuously increased creatinine values due to medical condition  Treatment required and laboratory values clinically significant	Renal impairment
Acute renal dysfunction	Creatinine value temporarily over 2.5 mg/dL  Possible actions: Fluid administration; adjustment of TAC/CsA or co-medication	Renal impairment
Severe renal dysfunction	Creatinine value stable over 2.5 mg/dL  Treatment required, but adjustment of TAC/CsA or co-medication not effective anymore; CNI toxicity	Renal impairment
Chronic severe renal dysfunction or Renal failure	Creatinine value stable over 2.5 mg/dL Dialysis or renal transplantation required	Renal impairment Renal Failure

Terminology of renal disorders table is prepared in accordance with Dictionary MedDRA - 23.1

#### 13.1.6 Vital Signs

Vital signs will be assessed at each visit.

The following vital signs will be recorded:

Systolic and diastolic blood pressure (sitting, after 5 minutes of rest), pulse rate (sitting, after 5 minutes of rest), body temperature (the same method should be used for each patient and throughout the clinical trial), and respiratory rate.

Abnormal values will be summarized by Common Toxicity Criteria (CTC) AE grade (version 5.0) for each patient.

#### 13.1.7 Physical Examinations

A physical examination will be carried out at the Screening Visit and at every subsequent visit. The following body systems will be examined: body weight, cardiovascular, respiratory, nervous, gastrointestinal, hepatic, renal, dermatological, musculoskeletal, extremities, eyes, ears, nose, throat, and lymphatic. Patient height will be measured at Screening Visit only.

Abnormal findings will be summarized for each patient.

#### **13.2** Data Monitoring Committee (DMC)

An independent Data Monitoring Committee will be established to monitor the safety of IMP throughout the studies BT – L-CsA – 301 – SLT and BT – L-CsA – 302 – DLT. The DMC will monitor safety by evaluating the safety analysis generated by the unblinded independent statistician during the course of the clinical trial. Details of the safety analyses will be included in the DMC's Charter. The DMC will evaluate treatment groups for possible trends in adverse events, determine whether the basic clinical trial assumptions remain valid, evaluate whether the overall integrity, scientific merit and conduct of the clinical trial remain acceptable, and make recommendations to the Sponsor.

The DMC will perform a comparison between the rate of observed COVID-19 cases, rate of patient's withdrawal, and rate of missing data among trial participants in both treatment arms.

Members of the DMC will be unblinded to the treatment group label, i.e., the DMC will know which group is L-CsA + Standard of Care and which group is Standard of Care alone. The DMC will evaluate all safety and acute tolerability parameters, to be detailed in the DMC charter.

Safety and acute tolerability parameters include adverse events, acute tolerability of L-CsA, infections, malignancies, clinical laboratory data (white blood cell count with differential, red blood cell count, platelet count, alkaline phosphatase, alanine aminotransferase, aspartate aminotransferase, gamma glutamyl transferase, blood urea nitrogen, serum bilirubin, serum creatinine), vital signs, physical examinations and FEV1. The statistics provided will be merely descriptive.

#### 13.3 Adjudication Committee (AC)

The AC – consisting of three independent physicians, with documented expertise in the clinical management of lung transplantation and diagnosis and treatment of BOS - will maintain the role of reviewing the BOS progression data in blind condition once each participating subject completes the study period, with the aim to ensure consistent and complete recording of data. If necessary, the AC may query the sites to ask for clarifications.

In case there are discrepancies between the assessment of the AC and that of the investigator re: BOS progression events, the CRO will notify the investigator. In all cases, the final decision as to whether or not specific event qualifies as BOS progression stands with the Investigator.

Details of the AC activities will be included in the AC's Charter.

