#### 9.3.1 Blinding

The pulmonary function technicians, respiratory therapists, or physiotherapists who conduct spirometry on site will be blinded to treatment assignment. Patients and other unblinded personnel will be asked to not share treatment assignment information with the pulmonary function technicians, respiratory therapists, and physiotherapists. The statistician who performed the interim sample size re-assessment was blinded to study treatment assignment. For details of the blinding of the Data Monitoring Committee members, see Section 13.2. For details of the blinding of the Adjudication Committee members, see Section 13.3. Clinical trial monitors, treating physicians, study nurses, study coordinators, and enrolled patients will not be blinded to study treatment assignment.

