#### 7.2 Randomization and Stratification

At the Baseline visit (V1), after all inclusion and exclusion criteria have been fully evaluated, eligible patients will be randomized with equal probability to one of two treatment arms, a control arm (SoC alone) and an investigational arm (L-CsA plus SoC). The investigational medicinal product (IMP) is L-CsA. To assure balance between treatment arms with regard to key variables and potential confounders, stratification prior to randomization will be performed for the following variables:

- Screening FEV1 ≥81% of personal best FEV1 value post-transplant versus Screening FEV1 between 80-51% of personal best FEV1 value post-transplant;
- Age at the time of randomization: <55 years versus ≥55 years;

- · Region: North America versus all other countries together.

Within each of the 8 strata, patients will be randomly assigned with equal probability (1:1) to either the investigational or control arm using a permuted blocks randomization. The randomization code, including specification of the block size, will be generated by a statistician not otherwise involved with the trial, using validated software. The unique randomization number and treatment assignment of each patient will be provided to the Investigator through the electronic Case Report Form (eCRF) after eligibility has been verified. The number assigned to a patient will be that patient's unique identifier throughout the clinical trial and cannot be re-assigned to another patient.

This is an open-label clinical trial. Clinical trial monitors, treating physicians, study nurses, study coordinators, and enrolled patients will not be blinded to treatment assignment.

[figure not shown]

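### The blinded Adjudication Committee is only advisory: the unblinded investigator has the final decision on BOS progression, so disputed events rest on a call made with knowledge of the arm

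*Protocol*

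**What the plan says.** Protocol 13.3 sets up an Adjudication Committee (AC) of three independent physicians. Its task is "reviewing the BOS progression data in blind condition once each participating subject completes the study period". The purpose given for this review is data quality: "with the aim to ensure consistent and complete recording of data". It may query the sites. If its assessment differs from the investigator's, "the CRO will notify the investigator". The rule that then applies, without exception, is that "the final decision as to whether or not specific event qualifies as BOS progression stands with the Investigator". The protocol synopsis and SAP 8.6 repeat it.

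On blinding, SAP 7.2 states: "This is an open-label clinical trial". Under the same section the investigator receives each patient's assignment through the eCRF. Protocol 9.3.1 adds: "Clinical trial monitors, treating physicians, study nurses, study coordinators, and enrolled patients will not be blinded to study treatment assignment". On-site spirometry staff are blinded (Protocol 9.3.1), and all maneuvers are centrally over-read (Protocol 12.1.1).

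Protocol 12.1.2 gives four routes to progression: a confirmed FEV1 fall together with a second spirometric criterion, a worse BOS grade, re-transplantation, or death from respiratory failure. The investigator reports the event in the eCRF.

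**The concern.** A blinded committee protects an endpoint in an open-label trial when its classification decides, or at least feeds a named analysis. Here its visible effect on a disputed event is a notification. The investigator then decides, after the patient has completed the study period and knowing the arm.

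Protocol 9.2 argues that the open-label design carries little risk of bias. Its main supports are the objectivity of FEV1, blinded technicians and central reading, and its conclusion is confined to the primary outcome. No equivalent case is made for BOS progression.

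At stake is the credibility of time to BOS progression. The SAP treats it as an endpoint (version history; censoring rule in 9.5.1) and compares the arms on it by log-rank test within subgroups (14.6). A favourable result would invite the question of how many events turned on the unblinded call, and no visible output answers it.

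**Working it through.** **1. No plan figure to reproduce.** No progression risk, event count or power for BOS progression is visible. The stated sample size (50 per arm, Protocol 15.5) concerns FEV1 and has no bearing here.

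**2. Where knowledge of the arm can enter.** Taking the four routes in Protocol 12.1.2 in turn:

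| Route | What settles it | Room for an arm-aware decision |
|---|---|---|
| Confirmed FEV1 fall plus second criterion | Numbers obtained by blinded staff and over-read centrally | Little in the values. Some in whether and when confirmation happens: the measurements must be at least 2 weeks apart, scheduled visits are 4 to 8 weeks apart, and the investigator may call unscheduled visits (14.2.7) |
| Worse BOS grade | FEV1 as a percentage of personal best (Table 3); historical personal best documented at Screening (14.2.1) | Little |
| Re-transplantation | Date of surgery (12.1.4) | Little |
| Death from respiratory failure | Attribution of cause | Clear |

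Two further openings apply to every route: the investigator reports the event, and the investigator decides whether to change the call after a discrepancy notice.

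**3. What a small directional shift would do (assumed inputs).** The documents give neither the progression risk nor the disagreement rate. Assume the same true risk p in both arms, proportional hazards, and a net shift of s percentage points: events added in SoC and removed in L-CsA. Then

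HR = ln(1 − p + s) / ln(1 − p − s)

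| True risk p | s = 2 points | s = 5 points |
|---|---|---|
| 30% | ln(0.72)/ln(0.68) = 0.85 | ln(0.75)/ln(0.65) = 0.67 |
| 40% | ln(0.62)/ln(0.58) = 0.88 | ln(0.65)/ln(0.55) = 0.72 |
| 50% | ln(0.52)/ln(0.48) = 0.89 | ln(0.55)/ln(0.45) = 0.75 |

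At p = 40%, a 2-point shift is 2/40 = 5% of the events in each arm, and a 5-point shift is 5/40 = 12.5%.

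**4. Effect on false positives (assumed inputs).** The SAP reports 169 patients randomized, so about 84 per arm. Treat progression as binary with no true effect, leave SoC untouched, and let a share x of the L-CsA events be reclassified as non-events. With p1 = p, p2 = p(1 − x), mean risk m = (p1 + p2)/2, SE0 = √[2m(1 − m)/84] and SE1 = √[(p1(1 − p1) + p2(1 − p2))/84], the one-sided error at nominal 0.025 is Φ[(p1 − p2 − 1.96·SE0)/SE1]. For p = 0.40 and x = 0.05: (0.02 − 1.96 × 0.0753)/0.0753 = −1.69, giving 0.045.

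| Share x | p = 30% | p = 40% | p = 50% |
|---|---|---|---|
| 5% | 0.040 | 0.045 | 0.051 |
| 10% | 0.063 | 0.077 | 0.095 |
| 20% | 0.139 | 0.189 | 0.254 |

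Both tables show only how sensitive the endpoint is to net reclassification in one direction. Neither estimates what will happen in this trial.

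**The case against.** The strongest defence has four parts.

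- **Most of the definition is measured, not judged.** FEV1 decline and BOS grade are arithmetic on blinded, over-read spirometry, and re-transplantation is a fact. The clearly judgemental component is cause of death, and Protocol 15.2.3.1 expects deaths and re-transplantations to be rare. This stands. It narrows the exposure and makes the larger shifts above look severe, but it does not remove discretion over reporting, confirmation and the response to discrepancies.
- **The AC was set up for data quality, and the rule matters only on disagreement.** A reader might infer that the investigator overrules the committee on every event. The documents do not say that. They give the investigator final authority, which has effect only where the two differ, and an investigator may change the call after a query or notice.
- **The decisive text is not visible.** SAP 14.4.2 is redacted, its version history records added sensitivity analyses there, and the AC Charter is not supplied. A reader might infer that no AC-based or programmed analysis exists, or that the blinded review cannot protect the endpoint at all. Neither can be concluded. What can be read is the rule in SAP 8.6, which names no analytical use of the AC's assessment.
- **The AC's assessment may not be ready for analysis.** The documents do not show that it records event dates. This is fair and affects the cost of the fix.

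**Conclusion.** The point holds in a limited form. Both documents state a rule under which a disputed progression event is settled by someone who knows the arm, while a blinded assessment of the same data is made and has no stated role in the analysis. This is an avoidable route to bias on a non-primary endpoint, and it merits correction. Whether the endpoint sits in the confirmatory hierarchy is redacted (Protocol 15.2.3.3, SAP 8.4).

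The primary endpoint is untouched: SAP 14.1.1 uses only accepted over-reader FEV1 values, which do not pass through this decision.

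The size is unknown. At an assumed 40% risk with no true effect, hazard ratios of 0.88 to 0.72 follow from net shifts of 2 to 5 points per arm in opposite directions. A reader might take this as evidence that results will favour L-CsA. That direction is plausible in an open-label add-on trial, but nothing in the documents demonstrates it. If disagreements are few or balanced between arms, the effect is negligible.

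**What to change.** **Preferred.** In the SAP, define the event for time to BOS progression by the blinded AC classification, or by a programmed derivation from over-read spirometry for the spirometric components with the AC classifying the rest. Use the investigator's classification as a sensitivity analysis.

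**Minimum.** Unless SAP 14.4.2 already does so, add an AC-based analysis and tabulate AC–investigator disagreements by arm, by direction (event added or removed) and by component. Show the investigator's call before and after the notice. If 14.4.2 or the AC Charter already covers this, a cross-reference in SAP 8.6 closes the point.

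**Cost.** SAP wording, one further analysis and one table, with no change to patient procedures. The preferred option departs from the rule that the investigator decides in all cases, so it must be documented in SAP section 16 and explained in the study report, as Protocol section 15 requires. The AC must record event dates, which may mean revisiting completed reviews. Event counts may differ from those in the eCRF. The change should be made before database lock and before any comparative results are seen.

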#### 14 VISIT SCHEDULE

All clinical trial visits, investigations and activities are listed in the Clinical Trial Schedule of Activities below. Further details on the methodology of these investigations and activities are described in detail in Section 12 and 13. The investigator will adhere to the visit and procedure schedule as closely as possible.

All patients assigned to a randomization number will be followed according to the protocol unless consent for follow-up is withdrawn. The Sponsor must be notified of all deviations from the protocol visit schedule or evaluations, and these visits/evaluations, if applicable, must be rescheduled or performed at the closest possible time to the original schedule.

For all patients randomized to L-CsA, proper patient understanding and competency of the competency of the use will be ensured in an individual training by the responsible clinic personnel. The patient will be administering the drug independently under supervision to verify patient competency with the equipment and drug tolerability.

After randomization, patients will visit the clinic every 4-8 weeks throughout the 48-week duration of the treatment period.

It is recommended that the Investigators contact the patient approximately 1 to 2 weeks prior to the next visit to remind the patient about the next scheduled visit. Patients will be instructed to call clinical trial personnel to report any abnormalities, including any hospitalizations or doctor visits during the interval between visits and to come to the clinical trial site if medical evaluation is needed and urgency of the situation permits. For emergency and other unscheduled visits to a medical facility other than the clinical trial site, medical records of the visit should be obtained by the Investigator.

If a patient prematurely discontinues clinical trial participation for any reason apart death, retransplantation or withdrawal of consent, he/she will be encouraged to complete the follow-up

Protocol Number: BT – L-CsA – 302 – DLT

L-CsA: Treatment of BOS after DLT Sponsor: Zambon SpA

visits planned in the protocol. All patients who prematurely discontinue the study, including the ones who undergo re-transplantation or withdraw their consent for further participation in the clinical trial, should complete at least the evaluation listed under "End of Treatment Visit" (Visit 9) prior to discontinuation whenever possible (the reason for premature withdrawal should always be documented).

